10.0 Study Design / Methods

Entryway Intake. All participants will complete a centralized Entryway Intake process for substance use studies at MUSC (i.e., the Entryway Intake (PRO #94743)) to determine eligibility before consenting for this project. This triaged approach allows for minimization of participant study shopping ("professional participants") and assurance that participants are triaged to the most appropriate study, thereby increasing the confidence and validity of study-specific results¹⁰⁴⁻¹⁰⁶. Eligibility criteria for all Youth Collaborative studies (including the proposed study) will be concurrently assessed during the Intake and participants will only be offered study participation in studies for which they are eligible.

Overview. Our primary goal is to test CBD as a potential candidate medication for youth with AUD, leveraging neuroimaging and behavioral data, to examine the acute neurometabolic, neurobehavioral, and psychophysiological effects. In counterbalanced order, youth (ages 16-22; 50% female) will receive 600 mg of CBD²⁵⁻³⁰ or matched placebo with a standardized snack, separated by approximately 18 days³¹ (see Figure below). We will stratify by education level (high school vs post high school) to ensure that these developmental groups are represented equally between the randomized crossover orders within our final sample. Neuroimaging will be collected after each medication trial: MRS will examine glutamate and GABA levels in the anterior cingulate cortex, and fMRI alcohol cue reactivity will examine neural response in reward networks, post-CBD and placebo. *In vivo* response to olfactory alcohol cues will be measured via heart rate, skin conductance, and subjective ratings⁸⁵.

Participant Procedures

CBD or placebo administration. This double blind crossover trial will compare acute oral CBD (600 mg^{25-27,29}) and placebo, followed by an approximate 18 day washout to allow for CBD clearance³¹ (terminal half-life 18-32 hours after acute oral dose)⁹³. All participants will eat a standardized snack with each medication administration. Neuroimaging will be conducted 3 hours after CBD/placebo administration to allow for CBD to reach its peak plasma concentration^{26,101}. Medication response and tolerability/adverse events will be assessed at each visit.

Assessments

We focused on inclusion of measures that are standardized for this age group, have good psychometric properties, and/or are part of the PhenX Toolkit or are included in the multisite Adolescent Brain and Cognitive Development study to yield comparable data to national datasets. See **Study Timetable (Table 1)**.

Clinical assessments. In general, these measures will be used to assess and track mental health and substance use-related problems over the course of study participation. Adverse events will be documented, rated for severity and relatedness, and managed/reported appropriately via established procedures. Participants will also meet with a medical clinician at each in person study visit to ensure physical and mental wellbeing throughout the study.

Primary Assessments: Entryway Intake Process (PRO #94743)

Physiological and Biological Assessments

Urine samples will be obtained from all participants to conduct pregnancy tests (female sex at birth only) and qualitative urine drug screens. For females, the pregnancy test will be completed first and a positive pregnancy test will immediately stop all subsequent procedures. No urine drug screen will be completed. An alcohol breath sample will be obtained from all participants to rule-out acute intoxication. A carbon monoxide sample will be collected via a carbon monoxide monitor. A saliva sample will be collected for profiling of microbial communities via 16S rRNA sequencing. Vital signs will be taken on all participants, including height, weight, blood pressure, and pulse.

Self-Report Measures

1. The Demographic Form was designed by our research team to assess basic demographics, including age, gender, race, and social history.
2. The MacArthur Social Status Ladder is a brief, 2-item measure with good psychometric properties (Operario, Adler, & Williams, 2004). It is designed to assess how individuals perceive their relative status in their community and nationally.

3. The Health and Substance Use History Questionnaires were designed by our team to assess basic health functioning and lifetime substance use exposure. Age of substance use onset will also be detailed.
4. The Treatment Services Utilization Forms were designed by our research team to assess history of substance use and psychiatric treatment utilization.
5. The Pittsburgh Sleep Quality Index (PSQI; Buysee et al., 1989) is a brief instrument designed to assess typical duration and quality of sleep.
6. The Quality of Life Enjoyment and Satisfaction Questionnaire (Q-LES-Q-SF; Schechter, Endicott, & Nee, 2007) and the Pediatric Quality of Life Enjoyment and Satisfaction Questionnaire (PQ-LES-Q-SF; Endicott, et al., 2006) are 16-item and 15-item measures, respectively, designed to assess the degree to which one experiences joy and satisfaction. The pediatric version will be administered to youth ages 12-17, and the adult version will be administered to participants ages 18 and older.
7. The Everyday Discrimination Scale – Short Version (Williams et al., 1997) is a 6-item measure designed to assess experiences of discrimination due to race, ethnicity, gender, disability, physical appearance, or other attributes.
8. The Beliefs about Medicines Questionnaire (Horne et al., 1999) subscale related to general beliefs will be administered to assess attitudes toward medications. Three positively valanced items regarding medications were created by the study team and added to the measure, resulting in 11 total questions.
9. The Mini International Neuropsychiatric Interview (MINI; Sheehan et al., 1998; Sheehan et al., 2010) is a semi-structured interview designed to assess current, past, or lifetime history of major DSM 5 psychiatric and substance use disorder diagnoses. Based on the original MINI, an expanded version (MINI Plus) and a pediatric version (MINI Kid) have been developed and validated. The appropriate instrument (MINI Plus for participants ≥ 18 years and MINI Kid for participants < 18 years) will be administered by trained staff.
10. The Patient Health Questionnaire (PHQ-9; Kroenke et al., 2001) is a 9-item scale used to assess DSM-IV symptoms of depression.
11. The Generalized Anxiety Disorder scale (GAD-7; Spitzer et al., 2006) is a 7-item measure used to assess symptoms of generalized anxiety.
12. The UPPS-Revised-Child Impulsivity Scale (Zapolski et al., 2010; Gunn et al., 2010) is a 40-item measure used to assess five facets of trait impulsivity among youth (administered to participants ages 12-25).
13. Difficulties in Emotion Regulation Scale Short Form (DERS-SF; Kaufman, et al., 2015) is an 18-item self-report measure designed to assess six facets of emotion regulation problems among adolescents and adults: lack of emotion regulation strategies, non-acceptance of emotions, difficulties in goal-directed behavior, impulse control difficulties, lack of emotional awareness, and lack of emotional clarity.
14. Mental Health Treatment Utilization Form. This assessment includes a series of questions adapted from the National Survey on Drug Use and Health (a nationally representative SAMHSA-administered study) designed to assess adolescent current, past year, and lifetime mental health service utilization and reasons for service utilization.
15. The Eating Disorder Screen for Primary Care (ESP) (Cotton et al., 2003) is a 5-item measure to quickly screen for the presence of an eating disorder.

16. The Timeline Follow Back (TLFB; Sobell & Sobell, 1992) is a calendar-based assessment designed to enhance retrospective recall of substance use for the past 60 days. Quantity and frequency of alcohol, cannabis, tobacco/nicotine products (cigarettes, ENDS, other tobacco/nicotine products), and other drug use will be assessed. Grams of cannabis will be estimated. Cannabis Methods. This assessment is conducted concurrently with the TLFB and includes a series of questions to determine which routes of administration participants are employing to use cannabis.
17. The Rapid Eating Assessment for Participants- Shortened Version (REAP-S; Segal-Isaacson 2004) is a brief validated questionnaire designed to quickly assess nutrient intake.

Secondary Assessments: Entryway Intake Process

(The following measures will be administered depending on responses to TLFB):

18. The Marijuana Assessment Problem Inventory (MAPI; Johnson & White, 1989) is a 23-item scale assessing consequences of cannabis use. This will be administered if past 60-day cannabis use is endorsed on TLFB.
19. Rutgers Alcohol Problem Index (RAPI; White & Labouvie, 1989) is a 23-item questionnaire assessing consequences of alcohol use. This will be administered if past 60-day alcohol use is endorsed on TLFB.
20. The Stages of Change Readiness and Treatment Eagerness Scale (SOCRATES; Miller & Tonigan, 1996) is a 19-item questionnaire designed to assess readiness to change drug use. Instructions will be modified for cannabis and alcohol use. These will be administered if past 60-day cannabis or alcohol use is endorsed on TLFB, respectively.
21. Thoughts About Abstinence Scale (e.g., Substance Use Goals; Hall et al., 1991) assesses whether participants are interested in total abstinence, reduced use, or no change in substance use behavior for each of the following substances: alcohol, cannabis, e-cigarettes/nicotine vaping, regular cigarettes. There are 4 items in total (one for each substance).
22. Reasons for Quitting Questionnaire-Cannabis (Steinberg et al., 2005) is a 27-item scale designed to assess common reasons for wanting to quit using cannabis. The scale will be modified to reflect quitting or reducing cannabis use and will only be administered to participants who report an abstinence or reduced use goal for cannabis on the "Thoughts About Abstinence Scale". Note that only items 1-27 will be administered.
23. The Motivation to Quit Measure (Turner & Mermelstein, 2004) is a single item assessing motivation to quit smoking. This has been adapted to additionally assess motivation to quit vaping or e-cigarette use in the current study. These will be administered if past 60-day cigarette or e-cigarette use is endorsed on TLFB, respectively.
24. The Addiction Growth Mindset Questionnaire (Burnette et al., 2019) is a 3-item questionnaire designed to assess whether individuals see their substance use and behaviors as malleable or static in nature.
25. The Modified Fagerström Tolerance Questionnaire (mFTQ; Prokhorov et al., 2000) is a 7-item self-rating questionnaire assessing nicotine dependence in the adolescent population and it will be given to participants that endorse tobacco use in the past 60 days on TLFB.
26. Penn State Electronic Cigarette Dependence Index (Foulds et al., 2015) is a 10-item questionnaire assessing electronic cigarette dependence, given to participants that endorse past 60-day e-cigarette use on TLFB.

Additional Study Specific Assessments

27. Clinical Institute Withdrawal Assessment for Alcohol (CIWA): Alcohol withdrawal will be assessed at the beginning of each session using the CIWA. A score >10 will result in referral to a higher level of clinical care.
28. Columbia Suicide Severity Rating Scale assesses for suicidal ideation at each visit and if a higher level of clinical care is needed.
29. Prior/concomitant medication will assess for eligibility at each medication visit (see exclusion criteria).
30. Adverse events will be assessed after each medication dose.
31. Penetration of the Blind will be assessed after each medication dose to assess the participant's belief about whether they received the placebo or active condition.
32. Cash Choice task is a brief measure of motivation, inhibition, impulsivity.
33. Alcohol Purchase Task (17 items; Murphy et al., 2006) is a behavioral economic measure of motivation for alcohol.
34. Alcohol Urge Questionnaire (Drobes & Thomas, 1999) is a measure that assesses alcohol urges.
35. Barratt Impulsiveness Scale (BIS-11) is a 30-item self-report scale used to measure impulsiveness.

	Entryway Intake	Study Screener	Visit 1	Visit 2	Visit 3 (remote)
Study Visit Information					
Informed Consent	X	X			
Locator Form and Updates		X	X	X	X
Penetration of the Blind			X	X	
Demographics, Health, Experiences, and Functioning					
Demographics	X				
MacArthur Social Ladder	X				
Health and Substance Use History Questionnaires	X				
Treatment Services Utilization (substance use)	X		X	X	X
Treatment Services Utilization (mental health)	X				
Pittsburgh Sleep Quality Index	X		X	X	
Quality of Life Enjoyment and Satisfaction (Pediatric and Adult Versions)	X				
Everyday Discrimination Scale	X				
Beliefs About Medicines Questionnaire	X				
Biological Samples					
Pregnancy test	X		X	X	
Urine sample	X		X	X	
Alcohol breathalyzer	X		X	X	
Carbon monoxide sample	X				
Saliva sample	X		X	X	
Blood sample			X	X	
Medical Assessments					
Meet with Medical Clinician		X	X	X	X (optional)
Brief Medical History & Physical Exam		X			
Adverse Events		X	X	X	
Prior/Concomitant Meds		X	X	X	X

Clinical Institute Withdrawal Assessment for Alcohol		X	X	X	
Vitals Signs/Body Mass Index	X		X	X	
General Mental Health and Psychological Assessments					
MINI International Neuropsychiatric Interview-DSM 5	X				
MINI Alcohol Use Disorder Past 30 Day Module		X			
PHQ-9	X		X	X	
GAD-7	X		X	X	
UPPS-R-C Impulsivity Scale	X				
Difficulties in Emotion Regulation Scale Short Form (DERS-SF)	X				
Eating Disorder Screen for Primary Care (ESP)	X				
Barratt Impulsiveness Scale (BIS-11)		X			
Columbia Suicide Severity Rating Scale		X	X	X	
Cash Choice Task		X	X	X	
Substance Use					
TLFB (Past 60 Days at baseline & Past number of days since prior TLFB at visits 1, 2, & 3)	X		X	X	X
Cannabis Methods	X				
Rutgers Alcohol Problems Index (RAPI)	X				
Marijuana Assessment Problem Inventory (MAPI)	X				
SOCRATES (Alcohol)	X		X	X	
SOCRATES (Cannabis)	X				
Thoughts About Abstinence Scale (e.g., Substance Use Goals)	X				
Reasons for Quitting Questionnaire (Cannabis)	X				
Motivation to Quit (Cigarettes and E-cigarettes)	X				
Ecig Use Questionnaire	X				
Addiction Growth Mindset Questionnaire	X				
Modified Fagerström Tolerance Questionnaire	X				
Penn State Electronic Cigarette Dependence Index	X				
Alcohol Purchase Task		X	X	X	
Alcohol Urge Questionnaire			X	X	
Lab Procedures					
Alcohol Olfactory Cue Reactivity Task			X	X	
Magnetic Resonance Imaging			X	X	
Estimated Visit Length (hours)	2-3	1-1.5	5	5	0.5

Visits. On the day of the Entryway assessment, we will conduct an additional in-person Screening Visit, to set up and trial daily texting, ensure inclusion/exclusion criteria, and collect additional study-specific information. Visits 1 and 2 will be in-person and include neuroimaging. There will be a brief Visit 3 about two and a half weeks after Visit 2 that will be via phone or video to update the participant's information.

Daily texts. After Visits 1 and 2, participants will receive a daily text for the next 18 days with a maximum of 30 days if necessary due to scheduling. The text will have a link to an on-line REDCap survey that will ask about the prior day's use of alcohol, cannabis, tobacco, CBD, and other substances. The link can also be e-mailed if the participant prefers.

Alcohol cue exposure procedure. Consistent with published procedures utilized with youth at MUSC, all participants will undergo an olfactory alcohol cue exposure procedure⁸⁵ before the neuroimaging session. In a counterbalanced order, participants will smell water, a bottle or can of the participant's preferred alcoholic beverage, and a cup of apple juice (as this is not typically used as a mixer with alcohol¹⁰⁷) for three minutes each, with three minute rest periods in between each liquid. Heart rate, skin conductance, and self-reported craving (via the Alcohol Urges Questionnaire) will be acquired based on previously used protocols¹⁰⁷.

Biological assessments. Combined use of ethanol metabolites and traditional biomarkers [i.e. alcohol breathalyzer, urine ethyl glucuronide (EtG), and blood phosphatidylethanol (PEth)] will be utilized to corroborate self-report alcohol use¹⁰⁸⁻¹¹¹. THC and CBD assays will be collected through urine to corroborate cannabis use. Blood samples will also be used to detect peripheral cytokines. Saliva samples will be collected for profiling of microbial communities via 16S rRNA sequencing. Urine drug tests (comprehensive panel testing for cotinine, cannabinoids, amphetamines, opioids, and benzodiazepines) will be used to monitor other substance use. Urine pregnancy tests will be conducted with participants assigned female at birth. Participants will also be asked to sniff a scented candle and report whether they can smell it and identify the scent, to check basic ability to smell.

Neuroimaging protocol (1 hour).

Mock scanner: On Visit 1, participants will be introduced to the mock scanner to help them become acclimated to the MR environment and give them the opportunity to practice remaining still while in the magnet, which will minimize motion-related confounds in the imaging data.

Participants will undergo 2 neuroimaging scans (1 scan three hours after CBD, 1 scan three hours after placebo). Breath and urine toxicology samples will be collected before every scan. Saliva samples will be collected before and after every scan. Scans will be performed with a Siemens 3T Prisma^{fit} MRI scanner. Imaging sessions (~60 minutes) consist of:

1. **T1-weighted structural:** A high-resolution anatomical scan will be acquired, to allow subsequent registration to functional images and region-of-interest (ROI) definition.
2. **The Alcohol Cue Reactivity Task:**^{91,92} During the alcohol cue reactivity task, participants are shown pseudorandomly interspersed images of alcoholic (i.e., beer, wine, and hard liquor) and non-alcoholic (e.g., soft drink, juice) beverages, visual control images (i.e., blurred images), and a fixation cross. A magnetic fieldmap will also be acquired to allow geometric unwarping and cost-function masking of EPI images induced by magnetic field inhomogeneities.
3. **Magnetic Resonance Spectroscopy:** The magnetic resonance spectroscopy protocol proposed will be utilizing previously published methods.

Participants will be compensated \$25 for the Screening Visit, \$300 for completing both imaging visits (\$150 V1 and \$150 V2), as well as an additional \$1 per day for submitting their daily text questionnaire for a maximum of 60 days total. Participants will also be eligible for a \$30 referral bonus for everyone they refer who successfully randomizes into this study. Mileage reimbursement will be available to participants who live >25 miles away; the current mileage reimbursement rate, which is updated each year by the state, will be offered.

11.0 Specimen Collection and Banking

Biological Assessments. Urine samples will be obtained from all participants to conduct pregnancy tests (only those assigned female at birth) and qualitative urine drug screens. Necessary pregnancy tests will be completed first and a positive pregnancy test will immediately stop all subsequent procedures. The Clinical Neurobiology Lab (CNL) at MUSC will analyze urine and blood samples (urine ethyl glucuronide (EtG)), and blood phosphatidylethanol (PEth)). CNL will also process and store blood samples for analysis or peripheral cytokines. Participants will provide saliva samples using all-in-one collection kits and the samples will be immediately stored in a freezer until analysis.

12.0 Data Management

All data will be managed via REDCap. Research staff and participants will enter data in REDCap; a secure, web-based application designed exclusively to support data capture for research studies. REDCap provides: 1) an intuitive interface for data entry (with data validation); 2) audit trails for

tracking data manipulation and export procedures; 3) automated export procedures for seamless data downloads to common statistical packages (SPSS, SAS, R); 4) procedures for importing data from external sources; and 5) advanced features, such as branching logic and calculated fields. These procedures are effective in minimizing data entry errors (e.g., missing or errant data). Direct entry of data by study participants (self-reports) will also be conducted in this study. This is done through a front-end survey interface that allows the participant to enter data on select questionnaires/assessments, but not access any other study records or data in REDCap. Server maintenance will be conducted by Information Technology Specialists at MUSC.

Accuracy and completeness of the data collected will be ensured by weekly review in team meetings. The REDCap system does not accept outliers, illogical response patterns, etc., thus minimizing data entry errors during participant direct entry. The PI will have weekly meetings with the research coordinator and research assistants to discuss qualitative comments received during data collection and any problems in data collection or entry. [name] will periodically examine the database to look for irregularities. Initial data analyses will examine distributions of variable scores and comparability of baseline characteristics across conditions in case analyses need to be adjusted for these characteristics. [name] will be responsible for maintaining signed consent forms as source documents for quality assurance review and regulatory compliance.

Data Analysis

Crossover designs are highly cost-efficient and powerful designs¹¹². Laboratory studies can enroll more participants and minimize statistical noise through greater experimental control³². The primary outcome measures of interest will be glutamate and GABA levels (MRS; Aim 1), alcohol cue reactivity (fMRI; Aim 2), and *in vivo* response to olfactory alcohol cues (heart rate, skin conductance, subjective rating; Aim 3). For all outcomes, a generalized linear mixed effects regression model will be developed accounting for clustering within subject. Additionally, study day (scan 1 vs. scan 2), condition (CBD vs. placebo), and condition order (CBD/placebo, placebo/CBD) will be included to ensure the crossover design and washout period were successful. During model development, random intercepts will be included to account for variations in baseline response levels for individual participants and random slopes to account for varying responses to treatment. For all models, baseline characteristics will be assessed for association with study outcomes (e.g., sex, baseline alcohol use rates, alcohol craving) and when significant, will be added in a covariate adjusted model. Model based interactions will assess any differential effect of sex on the relationship between medication condition and study outcomes.

Power and sample size. The proposed study is primarily powered to assess the relationship between treatment with CBD as compared to placebo on glutamate and GABA levels in the anterior cingulate (Aim 1) and neural response to alcohol cues (Aim 2). In a cross-over study of the effects of CBD as compared to placebo on glutamate in the hippocampus in a population of patients with schizophrenia, significant increases were found ($d= 0.48$; $p=0.035$)²⁵. To our knowledge, the effects of CBD on cue reactivity have not been assessed using fMRI. However, several studies have demonstrated that CBD can modulate resting-state^{28,29} or task-based^{5,27,30,113-116} BOLD signal under similar study design (acute dosing, 600 mg CBD) with sample sizes smaller than our proposed sample. Given limited literature in this area, we were not able to run a power analysis for Aim 3; this pilot study will provide data to power further analyses/effect sizes. Due to the number of tests run within the fMRI and MRS aims, the study will be powered at 80% with a corrected $\alpha=.0005$ (.05/100). Thus, in a crossover randomized controlled trial, **n=27 study completers** would be necessary. Although the proposed project is of relatively short duration (1.5 months), we anticipate an attrition rate of up to 7 participants (~23%) due to head motion or other artifacts, thus requiring a total of **n=50 participants enrolled and randomized**.

Rigor and Transparency. The proposed study is rigorous and will achieve robust and unbiased results by using explicit inclusion/exclusion criteria (commensurate with AUD trials for youth); use of validated measures and methods; explicit hypotheses and corresponding planned statistical analyses; power estimates; planned handling of retention/attrition and missing data; and careful consideration of potential

confounds. Key biological variables such as sex and age are considered and are incorporated into the proposed data analytic plan. All experimental details are reported in a detailed and fully transparent manner for replication.

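### The claim of 80% power at alpha = .0005 with 27 completers cannot be reproduced from the stated inputs, and the figures 27, 7, ~23% and 50 do not agree

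*Combined protocol and SAP*

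**What the plan says.** Everything on this point is in section 12.0 (Data Management), under Data Analysis, in the paragraph on power and sample size.

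- Scope: "The proposed study is primarily powered to assess the relationship between treatment with CBD as compared to placebo on glutamate and GABA levels" (Aim 1), and also neural response to alcohol cues (Aim 2). Only Aim 3 is exempted from the power claim.
- Effect size: one value, from an earlier crossover study of hippocampal glutamate in schizophrenia, where "significant increases were found ($d= 0.48$; $p=0.035"). For Aim 2 the plan says "To our knowledge, the effects of CBD on cue reactivity have not been assessed using fMRI". No effect size is given for GABA.
- Level and power: "the study will be powered at 80% with a corrected $\alpha=.0005$ (.05/100").
- Completers: "Thus, in a crossover randomized controlled trial, n=27 study completers would be necessary".
- Losses: "we anticipate an attrition rate of up to 7 participants (~23%) due to head motion or other artifacts".
- Enrolment: "thus requiring a total of n=50 participants enrolled and randomized". Sections 1.0, 5.0 and 6.0 repeat 50 without deriving it.

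The analysis paragraph just before it says "For all outcomes, a generalized linear mixed effects regression model will be developed accounting for clustering within subject". It names no significance level for judging the results.

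**The concern.** The paragraph reads as a chain in which effect size, level and power lead to 27 completers, and 27 completers and expected losses lead to 50 enrolled. Neither link can be followed.

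An alpha of .0005 is very strict, and 27 completers looks far too few for a standardised effect near 0.48 at that level unless the two visits are very highly correlated. The allowance of 7 participants is much too small to take 27 to 50.

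This is the trial's only sample-size justification, and the next paragraph of the protocol lists power estimates as evidence of rigour. If the 80% is taken at face value but true power is far lower, a null result on glutamate, GABA or cue reactivity could be read as evidence against CBD when the study had little chance of detecting the effect it cites.

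**Working it through.** **Inputs from the plan.** Alpha .0005 (.05/100, divided correctly); power 80%; d = 0.48; two-period within-subject crossover; 27 completers; up to 7 lost (~23%); 50 enrolled. The test, sidedness, scale of d and within-subject correlation are not given, so both sidednesses and both scales are shown.

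**1. Trying to reproduce 27.** For a paired comparison with effect d_z (mean difference over the SD of differences), the normal approximation is n = ((z_alpha + z_power)/d_z)². Two-sided at .0005 this is ((3.481 + 0.842)/0.48)² = 81.1, so 82. The exact paired t test (noncentral t, n − 1 df, noncentrality d_z√n) needs 88 completers two-sided (power .799 at 87) or 80 one-sided (.796 at 79). Neither gives 27.

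**2. Power and detectable effect at alpha .0005, exact t, two-sided (one-sided in brackets).** The count 43 is 50 − 7. The count 38 is 50 × 0.77 = 38.5, rounded down. The text supports either.

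| Completers | Power if d_z = 0.48 | d_z for 80% power | Correlation needed for 80% if 0.48 is on the raw SD |
|---|---|---|---|
| 27 | 10% (15%) | 0.94 (0.89) | 0.87 (0.85) |
| 38 | 22% (29%) | 0.76 (0.72) | 0.80 (0.78) |
| 43 | 29% (37%) | 0.71 (0.67) | 0.77 (0.75) |
| 50 | 38% (47%) | 0.65 (0.62) | 0.73 (0.70) |

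Using n − 2 df, to allow for a period term, changes the two-sided powers by 0.2 percentage points or less. The last column uses d_z = d/√(2(1 − ρ)), that is ρ = 1 − ½(0.48/d_z)². For 27 two-sided, ρ = 1 − ½(0.48/0.942)² = 0.87.

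**3. Raw-SD reading, two-sided .0005.** The correlations are assumptions; the documents give none.

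| Correlation | d_z | n = 27 | 38 | 43 | 50 |
|---|---|---|---|---|---|
| 0.5 | 0.48 | 10% | 22% | 29% | 38% |
| 0.7 | 0.62 | 27% | 51% | 61% | 74% |
| 0.8 | 0.76 | 50% | 79% | 87% | 94% |

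**4. If results were judged at two-sided .05 instead.** With d_z = 0.48, power is 67%, 82%, 87% and 91% at 27, 38, 43 and 50.

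**5. Two calculations that do land on 27.** The documents show neither.

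- Entering 0.48 as Cohen's f in a repeated-measures F test at .0005 (two measurements, correlation 0.5, λ = f²·n·2/(1 − 0.5)) gives .794 at 26 and .822 at 27. With two measurements and correlation 0.5, f = 0.48 equals a paired effect of 0.96, twice the cited d.
- An uncorrected one-sided .05 normal approximation gives ((1.645 + 0.842)/0.48)² = 26.8, so 27. The exact t test at that level has 78% power at 27 and needs 29.

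**6. Attrition.**

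- 27 + 7 = 34.
- 27/(1 − 0.23) = 35.06, so 36.
- 7/50 = 14%; 7/34 = 20.6%; 7/27 = 25.9%; 7/30 = 23.3%, but 30 is not a sample size stated anywhere in the plan.
- Going from 50 to 27 is a loss of 23, and 23/50 = 46%.

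No combination of 27, 7 and ~23% leads to 50.

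**The case against.** The strongest reply is that the power half shows missing inputs, not wrong arithmetic. The plan cites 0.48 as prior evidence and never calls it the planning effect. A raw-SD effect of 0.48 with a correlation near 0.87, or an undisclosed planning effect near 0.94, would make 27 correct. Depending on assumptions, power with 38 to 50 completers runs from 22% to 94%, which shows that the reader cannot tell, not that the study is underpowered. This stands, and it is why the conclusion is limited to non-reproducibility. The raw-SD rescue is somewhat weakened because d = 0.48 with p = 0.035 is what a two-sided paired t test gives at n = 22 (p = .0352), which points to a paired effect. That is inference only, since the source sample size is not in the documents.

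Second, for fMRI the plan does disclose the gap and cites BOLD studies at the same dose with smaller samples, and it describes itself as a pilot. That is a rationale for feasibility, but it is not an effect size, and the 80% claim is still made for Aim 2.

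Third, 50 exceeds both 34 and 36, so the attrition mismatch does not leave the study short of its own target. This also stands: on its own, that mismatch is a documentation fault.

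Fourth, the report in section 2.0 of over 95% usable data does not contradict ~23%. It appears to count scans, whereas each participant here needs two usable ones, and the plan's figure is an upper limit. Nothing here depends on it.

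**Conclusion.** The concern holds. From the stated level, power and only effect size, 27 completers cannot be reproduced. If 0.48 is the paired effect and the test is two-sided at .0005, power at 27 is 10% and 80% needs 88 completers. With the 38 to 43 completers that the plan's own loss figures imply, an effect of that size would be missed 78% to 71% of the time, and 62% of the time even if all 50 completed. Those figures depend on the paired reading and on .0005 being the level at which results are judged. On the raw-SD reading with an assumed correlation of 0.8, power at 43 would be 87%. The 80% claim for GABA and cue reactivity has no effect size behind it on any reading.

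The attrition inconsistency needs no assumption: 27, 7, ~23% and 50 do not reconcile. Its consequence is limited to an enrolment figure with no shown derivation.

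**What to change.** In the power paragraph, state the planning effect and its scale (paired or raw SD), the within-subject correlation and its source if raw SD, the test, the sidedness, and whether results will be judged at .0005. Check the original calculation against the two possible origins of 27 in the working. If the documented inputs give 80% at 27, keep the claim and show the calculation. If not, replace it with wording such as:

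> At two-sided alpha = .0005, the paired effect detectable with 80% power is 0.76 with 38 completers, 0.71 with 43 and 0.65 with 50. No effect size was available for GABA or fMRI cue reactivity; these detectable effects are all that can be stated for them.

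Keep only the completer count that matches the reconciled attrition figure. Give that figure once, with its denominator and basis, and show how it leads from completers to 50 enrolled.

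The cost is protocol wording only, with no added participants and no change to the .05/100 correction. The downside is that the stated power may become less favourable if the inputs do not support 80% at 27.
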